7.4 Statistical Analyses for Safety

All safety analyses will be carried out for each study independently using the Safety Analysis Set for both the primary analysis and for the entire study. Analyses for Study 1 and Study 2 will be based on treatments the subjects actually received. Safety will be assessed by TEAEs, physical examination, laboratory assessments, and vital signs. The descriptive summary of subjects experiencing TEAEs by treatment group will be tabulated by the Medical Dictionary for Regulatory Activities primary system organ class and preferred term. In addition, summary of SAEs and TEAEs by severity and relationship to study drug as assessed by the Investigator will be provided. SAEs, severe TEAEs, or TEAEs that lead to premature study discontinuation will be listed. A similar summary will also be performed for AESIs.

The observed values for vital signs, physical examination, and clinical laboratory variables at each visit will be summarized. The number and percentage of subjects meeting the criteria for potentially clinically significant laboratory values will be summarized. Shift of laboratory values from Baseline to defined time points will be tabulated.

Missing safety data will not be imputed.

Analysis details will be specified in the SAP.

7.5 Interim Analysis

There are no interim analyses planned for efficacy endpoints. Information on the interim safety monitoring DMC is described in Section 6.3. A separate DMC charter will be prepared outside of the protocol and will describe the roles and responsibilities of the DMC members, frequency of data reviews, and relevant data to be assessed.

[figure not shown]
7.6 Multiplicity Adjustment and Overall Type I Error Control

All efficacy analyses including multiplicity adjustment will be carried out for Study 1 (bDMARD-IR AS) and Study 2 (nr-axSpA) separately. Study 1 and Study 2 will have its own hypothesis testing and overall type I error rate control at a level of 0.05 independently. Since all efficacy comparisons target superior efficacy from placebo, this is equivalent to a one-sided test at a level of 0.025.

A fixed sequence testing approach will be employed to control the familywise error rate at 0.05 level for the primary and multiplicity-controlled secondary endpoints. The test starts with the primary endpoint using two-sided $\alpha = 0.05$; significance can be claimed for a lower ranked endpoint only if the previous

[figure not shown]
endpoints in the sequence meet the requirement of significance. The testing sequence for Study 1 (bDMARD-IR AS) is shown in Figure 4. The testing sequence for Study 2 (nr-axSpA) is shown in Figure 5.

Figure 4. Testing Sequence for Study 1 (bDMARD-IR AS)

Note: The primary endpoint and all multiplicity-controlled secondary endpoints will be assessed at Week 14.

Figure 5. Testing Sequence for Study 2 (nr-axSpA)

* ASAS40 response at Week 52 is part of the testing sequence for EU/EMA regulatory purposes. For US/FDA regulatory purposes, the testing sequence stops at ΔMASES.

Note: The primary endpoint and multiplicity-controlled secondary endpoints will be assessed at Week 14 unless otherwise noted.

7.7 Sample Size Determination

The sample size and power were calculated for Study 1 and Study 2 separately. Power and sample size calculations were performed at two-sided significance level of 0.05 and accounting for a 10% dropout rate for Week 14 endpoints.

Study 1 (bDMARD-IR AS)

The planned total sample size of 386 subjects for this study (with a 1:1 randomization ratio for placebo and upadacitinib 15 mg) provides at least 90% power for the primary endpoint ASAS40 response of upadacitinib 15 mg versus placebo using a two-sided Chi-square test at 0.05 level. For ASAS40, the assumed response rates for upadacitinib and placebo are 24% and 6%, respectively.^{20,26,40} This sample size also provides 90% power for ASAS20, with assumed response rates for upadacitinib and placebo of 41% and 24%, respectively.

In addition, this sample size provides at least 80% power for several of the multiplicity-controlled secondary endpoints including change from Baseline in ASDAS, change from Baseline in MRI SPARCC score of spine, BASDAI 50 response, ASDAS ID, change from Baseline in Total Back Pain, change from Baseline in Nocturnal Back Pain, ASDAS LDA, change from Baseline in BASFI, and ASAS PR.^{20,26,40}

Study 2 (nr-axSpA)

The planned total sample size of 304 for this study (with a 1:1 randomization ratio for placebo and upadacitinib 15 mg) provides at least 90% power for the primary endpoint ASAS40 response of upadacitinib 15 mg versus placebo using a two-sided Chi-square test at 0.05 level. For ASAS40 at Week 14, the assumed response rates for upadacitinib and placebo are 42% and 17%, respectively.^{38,41,42,43}

In addition, this sample size provides at least 80% power for several of the multiplicity-controlled secondary endpoints including change from Baseline in ASDAS, change from Baseline in MRI score of SI joints, BASDAI 50 response, ASDAS ID, change from Baseline in Total Back Pain, change from Baseline in Nocturnal Back Pain, ASDAS LDA, ASAS PR, and Week 52 ASAS40 response (multiplicity-controlled for EU/EMA regulatory purposes).^{38,41,43}

8 ETHICS

8.1 Independent Ethics Committee/Institutional Review Board

The protocol, informed consent form(s), recruitment materials, and all subject materials will be submitted to the IEC/IRB for review and approval. Approval of both the protocol and the informed consent form(s) must be obtained before any subject is enrolled. Any amendment to the protocol will require review and approval by the IEC/IRB before the changes are implemented to a study. In addition, all changes to the consent form(s) will be IEC/IRB approved.

8.2 Ethical Conduct of the Study

Each study will be conducted in accordance with the protocol, operations manual, International Council for Harmonisation (ICH) guidelines, applicable regulations, and guidelines governing clinical study conduct and the ethical principles that have their origin in the Declaration of Helsinki. Responsibilities of the Investigator are specified in [Appendix B](#).

For subjects in Japan only: After marketing approval of upadacitinib for the treatment of nr-axSpA in Japan, M19-944 Study 1 and Study 2 will be conducted in compliance with the Ministerial on Good Post-marketing Study Practice (GPSP) in Japan.

In cases of COVID-19 pandemic situations leading to difficulties in performing protocol-specified procedures, AbbVie will engage with study site personnel in efforts to ensure the safety of subjects, maintain protocol compliance, and minimize risks to the integrity of the study while trying to best manage subject continuity of care. This may include alternative methods for assessments (e.g., virtual site visits), alternative locations for data collection (e.g., use of a local laboratory instead of a central laboratory), and shipping investigational product and/or supplies DTP to ensure continuity of treatment where allowed. Refer to the operations manual for additional details. In all cases, these alternative measures must be allowed by local regulations and permitted by the IRB/IEC. Investigators should notify AbbVie if any urgent safety measures are taken to protect the subjects against any immediate hazard.

8.3 Subject Confidentiality

For the protection of personal data, AbbVie has developed a robust security program focused on due diligence in design, managed change, and information security governance. Information Security policies govern the Information Security functions including identity and access management, operations, infrastructure, application, and third-party security requirements. The risk-based AbbVie Data Classification Tool dictates the level of scrutiny and control required for the relevant activities per AbbVie's Information Security policies taking into account the sensitivity of the data.

Before a subject's data are shared with AbbVie, the study investigator and staff will replace any information that could directly identify a subject (such as name, address, and contact information) with an assigned numerical study identifier or "code" which AbbVie cannot link to that subject's identity in order to protect the confidentiality of the data.

AbbVie has a data protection impact assessment program to ensure and document the appropriate controls and safeguards stated above are in place for clinical trial data that it controls and maintains and these processing activities respect privacy of clinical trial subjects. AbbVie also maintains robust security incident response policies and procedures, including requirements for the containment of any data related incidents, the mitigation measures where needed, and notification to authorities or affected individuals where required. During the COVID-19 pandemic, remote monitoring of data may be employed if allowed by the local regulatory authority, IRB/IEC, and the study site.

9 SOURCE DOCUMENTS AND CASE REPORT FORM COMPLETION

The Investigator is responsible for ensuring the accuracy, completeness, legibility, and timeliness of the data reported. All source documents should be attributable, legible, contemporaneous, original, accurate, and complete to ensure accurate interpretation of data. Clinical site monitoring is conducted to ensure that the rights and well-being of human subjects are protected, that the reported trial data are accurate, complete, and verifiable, and that the conduct of the trial is in compliance with the currently approved protocol, ICH Good Clinical Practice (GCP), and applicable local regulatory requirement(s). During the COVID-19 pandemic, remote data review and verification of data may be employed if allowed by the local regulatory authority, IRB/IEC, and the study site.

10 DATA QUALITY ASSURANCE

AbbVie will ensure that the clinical trial is conducted with a quality management system that will define quality tolerance limits in order to ensure human subject protection and reliability of study results. Data will be generated, documented, and reported in compliance with the protocol, ICH GCP, and applicable regulatory requirements.

11 COMPLETION OF THE STUDY

The start-of-study is defined as the date of the first site activated. For Study 1 and Study 2, the end-of-study is defined as the date of study participation by the last subject in the last country where the study was conducted. The end-of-study, as it pertains to Study Protocol M19-944, is defined as the end-of-study for Study 1 or Study 2, whichever is later.

APPENDIX A. STUDY SPECIFIC ABBREVIATIONS AND TERMS

Ab	antibody
AE(s)	adverse event(s)
ALT	alanine aminotransferase
AS	ankylosing spondylitis
ASAS	Assessment of SpondyloArthritis international Society
ASDAS	Ankylosing Spondylitis Disease Activity Score
ASQoL	Ankylosing Spondylitis Quality of Life
AST	aspartate transaminase
axSpA	axial spondyloarthritis
BASDAI	Bath Ankylosing Spondylitis Disease Activity Index
BASFI	Bath Ankylosing Spondylitis Functional Index
BASMI _{lin}	Linear Bath Ankylosing Spondylitis Metrology Index
bDMARD-IR	biologic disease-modifying antirheumatic drug inadequate responder(s)
bDMARDs	biologic disease-modifying antirheumatic drugs
CAC	Cardiovascular Adjudication Committee
CI	confidence interval
CMH	Cochran-Mantel-Haenszel
CRF	case report form
CRP	C-reactive protein
csDMARD(s)	conventional synthetic disease-modifying antirheumatic drug(s)
CXR	chest x-ray
CYP3A	cytochrome P450 3A isoform subfamily
DMC	Data Monitoring Committee
DTP	direct-to-patient
EC	Ethics Committee
eCRF	electronic case report form
EMA	European Medicines Agency
EQ-5D-5L	EuroQol 5 Dimensions 5 Levels Health State Instrument
EU	European Union
EudraCT	European Clinical Trials Database
FACIT-F	Functional Assessment of Chronic Illness Therapy-Fatigue
FDA	Food and Drug Administration

GCP	Good Clinical Practice
GI	gastrointestinal
GPSP	Good Post-Marketing Study Practice
HI	Health Index
hsCRP	High sensitivity C-reactive protein
ICH	International Council for Harmonisation
ID	Inactive Disease
IEC	Independent Ethics Committee
IGRA	Interferon Gamma Release Assay
IL	interleukin
INR	international normalized ratio
IRB	institutional review board
JAK	Janus kinase
KM	Kaplan-Meier
LDA	Low Disease Activity
MACE	major adverse cardiac event
MASES	Maastricht Ankylosing Spondylitis Enthesitis Score
Min	minimum
mm	millimeters
MMRM	Mixed Model for Repeated Measures
MRI	magnetic resonance imaging
mRNA	messenger ribonucleic acid
NA	not evaluable/assessable
nr-axSpA	non-radiographic axial spondyloarthritis
NSAID(s)	nonsteroidal anti-inflammatory drug(s)
NRS	numeric rating scale
PCR	polymerase chain reaction
PD Visit	Premature Discontinuation Visit
PED	Patient Experience Data
PGA	Physician's Global Assessment of Disease Activity
PK	pharmacokinetics
PPD	purified protein derivative (tuberculin)
PR	partial remission
PRO	patient-reported outcome

PsA	psoriatic arthritis
PtGA	Patient's Global Assessment of Disease Activity
QD	once daily
QoL	quality of life
RA	rheumatoid arthritis
SAE	serious adverse event
SF-36	36-Item Short Form Health Survey
SI	sacroiliac
SJC	swollen joint count
SpA	spondyloarthritis
SPARCC	Spondyloarthritis Research Consortium of Canada
TA MD	Therapeutic Area Medical Director
TB	tuberculosis
TJC	tender joint count
TNF	tumor necrosis factor
ULN	upper limit of normal
US	United States
VAS	visual analogue scale

APPENDIX D. ACTIVITY SCHEDULE

The following table shows the required activities across Screening and subsequent study visits. Activities are applicable for Study 1 and Study 2 unless specified. The individual activities are described in detail in the operations manual ([Appendix G](#)). Allowed modifications due to the COVID-19 pandemic are detailed within the operations manual.

Study Activities Table (Applicable for Study 1 and Study 2 unless specified)

Activity	Screening	Baseline	Wk 1	Wk 2	Wk 4	Wk 8	Wk 12	Wk 14	Wk 18	Wk 24	Wk 32	Wk 40	Wk 52	Wk 64	Wk 76	Wk 88	Wk 104	Unscheduled Visit	PD Visit	30-Day F/U Visit OR Phone Call	
		Day 1																			
INTERVIEWS & QUESTIONNAIRES																					
Subject information and informed consent	✓																	✓ (Remission-Withdrawal Period only)			
Eligibility criteria	✓	✓																✓ (Remission-Withdrawal Period only)			
Medical history	✓	✓																			
Drug and alcohol history	✓																				
Prior/concomitant therapy	✓	✓	✓	✓	✓	✓	✓	✓	✓	✓	✓	✓	✓	✓	✓	✓	✓	✓	✓	✓	✓
Latent TB risk assessment questionnaire	✓												✓					✓			
Review and document pregnancy avoidance recommendations with females of childbearing potential	✓	✓	✓	✓	✓	✓	✓	✓	✓	✓	✓	✓	✓	✓	✓	✓	✓	✓	✓	✓	
PRO																					
BASDAI, Total Back Pain, BASFI, PtGA, Patient's Global Assessment of Pain	✓	✓	✓	✓	✓	✓	✓	✓	✓	✓	✓	✓	✓	✓	✓	✓	✓	✓		✓	
Nocturnal Back Pain		✓	✓	✓	✓	✓	✓	✓	✓	✓	✓	✓	✓	✓	✓	✓	✓	✓		✓	
ASQoL, SF-36		✓	✓		✓	✓		✓		✓		✓	✓				✓		✓		

Activity	Screening	Baseline	Wk 1	Wk 2	Wk 4	Wk 8	Wk 12	Wk 14	Wk 18	Wk 24	Wk 32	Wk 40	Wk 52	Wk 64	Wk 76	Wk 88	Wk 104	Unscheduled Visit	PD Visit	30-Day F/U Visit OR Phone Call
		Day 1																		
ASAS HI		✓	✓	✓	✓	✓		✓		✓			✓				✓		✓	
FACIT – F		✓		✓				✓		✓		✓	✓				✓		✓	
EQ-5D-5L		✓		✓				✓		✓			✓				✓		✓	
WPAI		✓						✓		✓			✓				✓		✓	
PED questionnaire		✓																		
Subject diary		✓	✓	✓	✓	✓	✓	✓	✓	✓	✓	✓	✓	✓	✓	✓	✓	✓	✓	
 EXAM																				
Body weight	✓	✓			✓	✓	✓	✓	✓	✓	✓	✓	✓	✓	✓	✓	✓	✓	✓	✓
Height		✓																		
Vital signs	✓	✓	✓	✓	✓	✓	✓	✓	✓	✓	✓	✓	✓	✓	✓	✓	✓	✓	✓	✓
Physical exam	✓	✓						✓		✓			✓		✓		✓		✓	
MRI of spine and SI joints (prior to or at the scheduled visit)	✓							✓									✓		✓	
12-lead ECG (annually at Week 52 and Week 104 if required by country regulatory authorities)	✓												✓				✓		✓	
AE assessment	✓	✓	✓	✓	✓	✓	✓	✓	✓	✓	✓	✓	✓	✓	✓	✓	✓	✓	✓	✓
Investigator assessments: TJC/SJC		✓						✓		✓			✓		✓		✓		✓	
Investigator assessments: BASMI _{lin}		✓						✓		✓			✓		✓		✓		✓	

Activity	Screening	Baseline	Wk 1	Wk 2	Wk 4	Wk 8	Wk 12	Wk 14	Wk 18	Wk 24	Wk 32	Wk 40	Wk 52	Wk 64	Wk 76	Wk 88	Wk 104	Unscheduled Visit	PD Visit	30-Day F/U Visit OR Phone Call
		Day 1																		
Investigator assessments: MASES		✓			✓	✓		✓		✓			✓		✓		✓		✓	
Investigator assessments: PGA		✓	✓	✓	✓	✓	✓	✓		✓		✓	✓		✓		✓		✓	
Anteroposterior (AP) pelvis x-ray	✓																			
Lateral cervical and lumbar – spine x-ray	✓																✓		✓	
CXR (annually after Week 52 if annual TB test is newly positive [seroconversion])	✓												✓				✓			
Physical activity device dispensation (Study 1 [bDMARD-IR AS] only; except in countries where the digital health technology device is not available or is not allowed to be used in the study by the local regulatory authority) (device is to be worn through Week 14)		✓																		
Collection of physical activity device (Study 1 [bDMARD-IR AS] only; only applies to countries where the digital health technology device is approved)								✓												

Activity	Screening	Baseline	Wk 1	Wk 2	Wk 4	Wk 8	Wk 12	Wk 14	Wk 18	Wk 24	Wk 32	Wk 40	Wk 52	Wk 64	Wk 76	Wk 88	Wk 104	Unscheduled Visit	PD Visit	30-Day F/U Visit OR Phone Call
		Day 1																		
Physical activity spinal range of motion tasks (Study 1 [bDMARD-IR AS] only; only applies to countries where the digital health technology device is approved)		✓	✓	✓	✓	✓	✓	✓												
ASDAS (CRP) calculation to determine eligibility for Remission-Withdrawal Period																✓	✓			
																				
Urine pregnancy test (for all female subjects of childbearing potential)		✓	✓	✓	✓	✓	✓	✓	✓	✓	✓	✓	✓	✓	✓	✓	✓		✓	✓
Dispense urine pregnancy tests for monthly home testing									✓	✓	✓	✓	✓	✓	✓	✓				
Dispense urine pregnancy tests for monthly home testing (subjects entering OLE in applicable countries; see Appendix F)																	✓			
Erythrocyte sedimentation rate	✓	✓	✓	✓	✓	✓	✓	✓	✓	✓	✓	✓	✓	✓	✓	✓	✓	✓	✓	✓
Beta-D-glucan (Japan only)	✓																			

Activity	Screening	Baseline	Wk 1	Wk 2	Wk 4	Wk 8	Wk 12	Wk 14	Wk 18	Wk 24	Wk 32	Wk 40	Wk 52	Wk 64	Wk 76	Wk 88	Wk 104	Unscheduled Visit	PD Visit	30-Day F/U Visit OR Phone Call
		Day 1																		
 CENTRAL LAB																				
FSH, HIV, HCV, serum pregnancy test	✓																			
hsCRP, clinical chemistry, hematology, urinalysis	✓	✓	✓	✓	✓	✓	✓	✓	✓	✓	✓	✓	✓	✓	✓	✓	✓	✓	✓	✓
TB test (QuantIFERON TB Gold test [or interferon gamma release assay equivalent such as T-SPOT test] and/or local PPD skin test, if required)	✓												✓				✓			
HBV (post-Baseline tests for subjects from Japan only)	✓						✓			✓	✓	✓	✓	✓	✓	✓	✓		✓	
HLA-B27		✓																		
Study 1 (bDMARD-IR AS) blood samples for upadacitinib PK assay (only in approximately 30% of subjects in select sites)				✓		✓	✓	✓											✓	
Study 2 (nr-axSpA) blood samples for upadacitinib PK assay (only in approximately 30% of subjects in select sites)				✓		✓		✓		✓		✓							✓	
 TREATMENT																				
Randomization/drug assignment		✓																		

Activity	Screening	Baseline	Wk 1	Wk 2	Wk 4	Wk 8	Wk 12	Wk 14	Wk 18	Wk 24	Wk 32	Wk 40	Wk 52	Wk 64	Wk 76	Wk 88	Wk 104	Unscheduled Visit	PD Visit	30-Day F/U Visit OR Phone Call
		Day 1																		
Dispense study drug		✓			✓	✓	✓	✓		✓	✓	✓	✓	✓	✓	✓		✓		
Dispense study drug (subjects entering OLE for applicable countries; see Appendix F)																	✓			

Optional Biomarker Sample Activities Table (Applicable for Study 1 and Study 2)

Activity	Screening	Baseline	Wk 1	Wk 2	Wk 4	Wk 8	Wk 12	Wk 14	Wk 18	Wk 24	Wk 32	Wk 40	Wk 52	Wk 64	Wk 76	Wk 88	Wk 104	Unscheduled Visit	PD Visit	30-Day F/U Visit OR Phone Call
		Day 1																		
Study 1 (bDMARD-IR AS) blood: (DNA/RNA/serum/plasma)		✓		✓				✓												
Study 2 (nr-axSpA) blood: (DNA/RNA/serum/plasma)		✓		✓				✓					✓							

Study Activities Table for Remission-Withdrawal Period (Prior to Retreatment)

Activity	Wk 110	Wk 116	Wk 122	Wk 128	Wk 140	Wk 152	Unscheduled Visit	PD Visit
INTERVIEWS & QUESTIONNAIRES								
Concomitant therapy	✓	✓	✓	✓	✓	✓	✓	✓
Review and document pregnancy avoidance recommendations with females of childbearing potential	✓	✓	✓	✓	✓	✓	✓	✓
PRO								
BASDAI, PtGA, Total Back Pain, BASFI, Patient's Global Assessment of Pain, Nocturnal Back Pain, ASAS HI	✓	✓	✓	✓	✓	✓	✓	✓
EXAM								
Body weight	✓	✓	✓	✓	✓	✓	✓	✓
Vital signs	✓	✓	✓	✓	✓	✓	✓	✓
Physical Exam				✓		✓		
AE assessment	✓	✓	✓	✓	✓	✓	✓	✓
Investigator assessments: TJC/SJC, BASMI _{in} , MASES, PGA	✓	✓	✓	✓	✓	✓	✓	✓
ASDAS (CRP) calculation to determine disease status	✓	✓	✓	✓	✓	✓	✓	
LOCAL LAB								
Erythrocyte sedimentation rate	✓	✓	✓	✓	✓	✓	✓	✓
Urine pregnancy test (for all female subjects of childbearing potential entering OLE for applicable countries; see Appendix F)						✓		
Dispense urine pregnancy tests for monthly home testing (subjects entering OLE for applicable countries; see Appendix F)						✓		

Activity	Wk 110	Wk 116	Wk 122	Wk 128	Wk 140	Wk 152	Unscheduled Visit	PD Visit
								
hsCRP	✓	✓	✓	✓	✓	✓	✓	✓
Clinical chemistry, hematology, urinalysis	✓	✓	✓	✓	✓	✓	✓	✓
HBV (post-Baseline tests for subjects from Japan only)		✓		✓	✓	✓		

Study Activities Table for Remission-Withdrawal Period (After Retreatment)

Activity	RT Baseline	RT Wk 4	RT Wk 8	RT Wk 12	RT Wk 16	RT Wk 24	RT PD Visit	RT 30-Day F/U Visit OR Phone Call
INTERVIEWS & QUESTIONNAIRES								
Concomitant therapy		✓	✓	✓	✓	✓	✓	✓
Review and document pregnancy avoidance recommendations with females of childbearing potential	✓	✓	✓	✓	✓	✓	✓	✓
Latent TB risk assessment questionnaire	Annually, at a retreatment visit that is closest to Week 156, if applicable							
PRO								
BASDAI, Total Back Pain, BASFI, PtGA, Patient's Global Assessment of Pain, Nocturnal Back Pain, ASAS HI		✓	✓	✓	✓	✓	✓	
Subject Diary	✓	✓	✓	✓	✓	✓	✓	
EXAM								
Body weight		✓	✓	✓	✓	✓	✓	
Vital Signs		✓	✓	✓	✓	✓	✓	
Physical Exam				✓		✓		
AE Assessment		✓	✓	✓	✓	✓	✓	✓
Investigator Assessments: BASMI _{lin} , MASES, PGA, TJC/SJC				✓		✓	✓	
CXR (annually if annual TB test is newly positive [seroconversion] or a positive response to TB risk assessment questionnaire)	Annually, at a retreatment visit that is closest to Week 156, if applicable							
LOCAL LAB								
Urine pregnancy test (for all female subjects of childbearing potential)	✓	✓	✓	✓	✓	✓	✓	
Dispense urine pregnancy tests for monthly home testing					✓			

Activity	RT Baseline	RT Wk 4	RT Wk 8	RT Wk 12	RT Wk 16	RT Wk 24	RT PD Visit	RT 30-Day F/U Visit OR Phone Call
Dispense urine pregnancy tests for monthly home testing (subjects entering OLE for applicable countries; see Appendix F)						✓		
Erythrocyte sedimentation rate		✓	✓	✓	✓	✓	✓	
 CENTRAL LAB								
hsCRP, clinical chemistry, hematology, urinalysis		✓	✓	✓	✓	✓	✓	
HBV (post-Baseline tests for subjects from Japan only)				✓		✓		
TB test (QuantIFERON TB Gold test [or interferon gamma release assay equivalent such as T-SPOT test] and/or local PPD skin test, if required)	Annually, at a retreatment visit that is closest to Week 156, if applicable							
 TREATMENT								
Dispense Study Drug	✓			✓				

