
Investigational Plan:
	
Study 1 (bDMARD-IR AS) is comprised of a 35-day Screening Period; a 14-week randomized, double-blind, parallel-group, placebo-controlled period (the Double-Blind Period); a 90-week open-label, long-term extension period (the Open-Label Extension Period); and a 30-day Follow-Up Visit (F/U Visit).
 
Study 2 (nr-axSpA) is comprised of a 35-day Screening Period; a 52-week randomized, double-blind, parallel-group, placebo-controlled period (the Double-Blind Period); a 52-week open-label, long-term extension period (the Open-Label Extension Period); and a 30-day F/U Visit.

	
In the Double-Blind Period for both studies, subjects will be randomized in a 1:1 ratio to 1 of 2 treatment groups:
 
Study 1 (bDMARD-IR AS):
 
 • Group 1: upadacitinib 15 mg QD (N = 193) • Group 2: placebo QD (N = 193) 
Study 2 (nr-axSpA):
 
 • Group 1: upadacitinib 15 mg QD (N = 152) • Group 2: placebo QD (N = 152) 
Subjects in the placebo group will be switched to upadacitinib 15 mg QD at Week 14 in the Open-Label Extension Period for Study 1 (bDMARD-IR AS) and Week 52 in the Open-Label Extension Period for Study 2 (nr-axSpA).
 
Remission-Withdrawal Period:
 
 • Subjects with an ASDAS (C-reactive protein [CRP]) < 1.3 at Week 104 and an ASDAS (CRP) < 2.1 at Week 88 will be eligible for the open-label remission-withdrawal period. Subjects will be followed and assessed for potential flare through Week 152. Subjects who flare during this period (flare defined as ASDAS [CRP] ≥ 2.1 at 2 consecutive visits, which are at least 2 weeks apart, or ASDAS [CRP] > 3.5 at one visit) will be eligible to receive open-label upadacitinib 15 mg QD for 24 weeks (re-treatment) from the timepoint of flare. Subjects who do not flare through Week 152 during the withdrawal period, will have reached the end of the study. • Subjects not eligible for the withdrawal period will have reached the end of the study after the 30 day follow-up visit. 
For subjects in Japan only: Upon marketing approval of upadacitinib for the treatment of nr-axSpA in Japan, M19-944 Study 1 and Study 2 will be changed from Phase 3 studies to post-marketing clinical studies in Japan.

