The AbbVie study team will be unblinded to perform the Week 14 primary analysis for both studies. Reporting will be performed independently for Study 1 and Study 2. For Study 1 and Study 2, the unblinding will take place after all subjects in the study have completed the Week 14 visit or have prematurely discontinued prior to Week 14. For both Study 1 and Study 2, sites and subjects will remain blinded to the Double-Blind Period treatment assignments for the duration of the study.

Information on the Data Monitoring Committee (DMC) and Cardiovascular Adjudication Committee (CAC) are described in Section 6.3 and Section 6.1, respectively.

See Section 5 for information regarding eligibility criteria and Section 5.8 for information on stratification.

The schematic of Study 1 and Study 2 is shown in Figure 1. Further details regarding study procedures are located in the operations manual (Appendix G).

For subjects in Japan only: Upon marketing approval of upadacitinib for the treatment of nr-axSpA in Japan, M19-944 Study 1 and Study 2 will be changed from Phase 3 studies to post-marketing clinical studies in Japan.

Remission-Withdrawal Period

[figure not shown]
Subjects in Study M19-944 from both Study 1 (AS bDMARD-IR) and Study 2 (nr-axSpA) who reach Week 104 on study drug (upadacitinib 15 mg QD) will be assessed whether they are in remission, with an ASDAS (CRP) < 1.3 at Week 104 and an ASDAS (CRP) < 2.1 at Week 88.

Subjects in remission at Week 104 will be eligible for the Remission-Withdrawal Period. Subjects will be followed without study drug treatment and assessed for disease flare through Week 152. Flare is defined as an ASDAS (CRP) \geq 2.1 at 2 consecutive visits, which are at least 2 weeks apart, or an ASDAS (CRP) > 3.5 at one visit. Subjects who flare will receive open-label upadacitinib 15 mg QD from the time of flare for 24 weeks (re-treatment) or longer per local country requirements (See Appendix F for more details).

Subjects who do not flare, will be followed without upadacitinib treatment until Week 152.

Subjects who are not in remission at Week 104 will complete the study after the 30 day follow-up visit OR, if applicable, will have the option to enter open-label treatment with upadacitinib until a predefined time period only per local country requirements (See Appendix F).

Figure 1. Study Schematic

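### Appendix D schedules no pregnancy test after the last re-treatment dose for women who finish outside the country extension

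*Protocol*

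**What the plan says.** Protocol Section 2.2 describes upadacitinib as teratogenic in animals. Section 5.2 requires women of childbearing potential to avoid pregnancy on drug and for at least 30 days after the last dose. Under Pregnancy, Section 6.1 has positive tests and confirmed pregnancies assessed from Screening through the final study visit.

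Appendix D sets out the testing in three tables.

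- **Main table.** The row "Urine pregnancy test (for all female subjects of childbearing potential" is ticked at Week 104, at the PD Visit and at the 30-day follow-up visit or call. At Week 104 the only kit row ticked is "Dispense urine pregnancy tests for monthly home testing (subjects entering OLE in applicable countries; see Appendix F".
- **After Retreatment table.** The same row is ticked from RT Baseline through RT Week 24 and at the RT PD Visit, and is blank under "RT 30-Day F/U Visit OR Phone Call". The general home-kit row is ticked only at RT Week 16. At RT Week 24 the ticked kit row is "Dispense urine pregnancy tests for monthly home testing (subjects entering OLE for applicable countries; see Appendix F".
- **Prior to Retreatment table.** The only test row is "Urine pregnancy test (for all female subjects of childbearing potential entering OLE for applicable countries; see Appendix F", ticked at Week 152. There is no 30-day column.

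**The concern.** The re-treatment course ends with a contact placed about 30 days after the last dose, when the pregnancy-avoidance period is closing. The main schedule uses the matching contact for a urine test, and the re-treatment schedule does not. Outside the country extension no kit is handed out at the end of dosing either, so learning of a pregnancy at that contact depends on what the woman reports, possibly by telephone.

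What is at stake is safety ascertainment. A conception late in re-treatment or soon after it could be reported late or not at all, and its outcome might not be collected. By then there is no dosing left to stop.

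**Working it through.** No sample-size or power figure bears on this point. The check is a column-by-column reading of Appendix D, followed by a short timing calculation.

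**Step 1. Count the ticks in the clinic urine-test row.**

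| Appendix D table | Columns | Ticked | Blank | 30-day contact |
|---|---|---|---|---|
| Main | 20 | 18 (Baseline, 15 weekly-numbered visits, PD, 30-Day F/U) | Screening, Unscheduled | present, test ticked |
| After Retreatment | 8 | 7 (RT Baseline, RT Weeks 4, 8, 12, 16, 24, RT PD) | RT 30-Day F/U | present, test blank |
| Prior to Retreatment | 8 | 1 (Week 152, extension entrants only) | the other 7 | no such column |

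**Step 2. Follow a woman who completes re-treatment outside the extension.** Her last scheduled test is at RT Week 24, taken here as the time of her last dose. After that visit she has 0 scheduled tests. At or after that visit she is given 0 kits. Some kits from RT Week 16 may be left over, but nothing schedules their use after dosing. Her one remaining contact, the RT 30-Day F/U, covers concomitant therapy, pregnancy-avoidance review and adverse events. A woman who stops early is less exposed, because the RT PD Visit has a test and Section 5.6 asks for that visit after she stops the drug.

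**Step 3. What a day-30 test would add.** Assumption, not in the documents: a urine test turns positive L = 14 to 21 days after conception. A test on post-dose day d then shows conceptions up to day d − L.

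- RT Week 24 (d = 0): conceptions up to 14 (or 21) days before the last dose. Those in the final 14 to 21 days on drug are not yet visible.
- RT 30-Day F/U (d = 30): conceptions up to day 30 − 14 = 16, or 30 − 21 = 9. This covers all of the late on-drug conceptions and 16/30 = 53% to 9/30 = 30% of the post-dose window.

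A day-30 test therefore improves ascertainment without covering the whole window. The case for it does not depend on the exact lag, because it only brings the re-treatment table into line with the main one.

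**Step 4. Withdrawal entrants after Week 104.** Section 4.1 lists a 30-day follow-up visit as part of each study and does not exclude them. The Synopsis says "Subjects not eligible for the withdrawal period will have reached the end of the study after the 30 day follow-up visit" and, of entrants who stay well, "Subjects who do not flare through Week 152 during the withdrawal period, will have reached the end of the study". Section 4.1 likewise says "Subjects who are not in remission at Week 104 will complete the study after the 30 day follow-up visit". These sentences say when each group completes the study. They do not say whether an entrant also has the main table's 30-day contact and its test.

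**The case against.** The strongest reply is that the blank is part of a deliberately reduced contact. The RT 30-Day F/U column carries only three ticks, all of which can be done by phone. Weight, vital signs and laboratory tests are blank there too, although the main 30-day column has them. The 30-day column in Appendix F has the same three ticks and no urine test. This stands as an account of the format, and it is why the point is a design choice and not a slip.

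It does not dispose of the point. The main 30-day column also allows a phone call and still ticks the test. The Appendix F parallel is incomplete: its combined 12-weekly and final-visit column ticks home kits, and only the study-drug row excludes the Final Visit, so on the face of the table those women leave with a kit. Appendix E also gives continued pregnancy monitoring during and after the Remission-Withdrawal Period as a reason for its table edits, which at least shows the intent.

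Two further replies stand. Cover already exists: tests through RT Week 24 and at the RT PD Visit, pregnancy-avoidance review at the 30-day contact, and reporting within 24 hours once the site is aware. The operations manual, where Appendix D says activities are detailed, was not available and may already schedule a test.

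A reader might also infer that the re-treatment table is stricter than the main one on home kits. It is not: at Week 104 the main table likewise gives kits only to extension entrants. The contrast is confined to the 30-day test.

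**Conclusion.** The point holds for women of childbearing potential who complete re-treatment outside the country extension: Appendix D gives them no scheduled pregnancy test after the last dose, where the main schedule gives one. It is a minor matter of safety ascertainment, and correcting it is a cheap improvement. The documents do not give the number of women, and none is estimated here.

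Two stronger readings are not supported. One is that the protocol breaks its own rule. Section 5.2 requires avoidance of pregnancy and Section 6.1 requires assessment of known pregnancies, but neither requires a test at 30 days. The other is that withdrawal entrants have no post-dose test after Week 104. The text leaves that open, so it calls for a clarification and is not a demonstrated gap.

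The conclusion rests on the tick marks as they appear in Appendix D, on RT Week 24 being about the time of the last dose, and on the operations manual not already adding a test.

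**What to change.** In the After Retreatment table, tick the existing urine test at the RT 30-Day F/U. Give one home kit to every woman of childbearing potential at RT Week 24 or the RT PD Visit, to be used and reported when that contact is by phone. The kit goes one step beyond the main table, which schedules the 30-day test but does not supply a kit at Week 104 outside the extension.

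Add one sentence, as a clarification, saying whether the main table's 30-Day F/U and its urine test apply to withdrawal entrants after Week 104. Carry the changes into the operations manual if they are not already there.

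The cost is one extra urine kit per woman, a table edit and that sentence. The contact already exists, so no visit is added.
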